3.3.4 Removal of patients from therapy or assessments

3.3.4.1 Removal of individual patients

An individual patient is to be withdrawn from trial treatment if the patient:

1. Withdraws consent for study participation, without the need to justify the decision.
2. Has radiologic documentation by CTscan or MRI of progressive disease ([Section 5.1.2](#)) and is no longer receiving clinical benefit, in the opinion of the investigator.
3. Can no longer be treated with trial medication for other reasons (e.g. AE, pregnancy, surgery, concomitant diagnoses, or concomitant therapies) or administrative reasons.
4. Is diagnosed with ILD
5. Has the need for further dose reductions considered necessary but not allowed according to the protocol ([Section 4.1.4](#))

Given the patient's agreement, the patient will undergo the procedures for treatment discontinuation and/or EoR as well as follow up such as vital status collection as outlined in the [flow chart](#) and [Section 6.2.3](#). For all patients the reason for withdrawal (e.g. adverse

events) must be recorded in the (e)CRF. These data will be included in the trial database and reported.

The sponsor may remove patients from the study after completion of the primary efficacy analysis if the patient has access to afatinib study treatment via options included but not limited to an alternative clinical trial, marketed product, an expanded-access program, named patient use program, or compassionate use protocol or other means based on local regulation. This may mean a change in packaging and labelling. The cost of any ongoing supply of study medication will be incurred by the sponsor until disease progression occurs. If a patient is removed from the study treatment, an end of treatment and a follow up visit 30 days later will be performed to ensure all adverse events are followed up and then the patient will be considered to have completed the trial.

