6.2.3.3.2 Follow-up for Overall Survival

All patients will be followed-up for overall survival at 90 days intervals after the EoR visit or last follow-up for progression visit (as specified in [Section 6.2.3.3.1](#)) until death, lost to follow-up or completion of the whole trial (as specified in [Section 8.6](#)) whatever occurs earlier. For patients who progressed on treatment, the observation period for overall survival starts after the EoR visit. For patients who have not progressed on treatment, this period starts after the last FU for progression visit.

These visits may also be performed by e.g. telephone interview or via written correspondence in case the patient is unable to visit the investigator.

The following information will be collected during the follow-up for survival period:

- Date of contact
- Further anti-cancer treatment: regimen and drug name, start and stop dates, reason for stopping this treatment and/or best supportive care (if applicable)
- Outcome event (e.g. death: Record date of and reason for outcome event)
- Follow-up of adverse events in case they were not yet recovered at EoR, and AESI or SAEs if assessed as related by the investigator.

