7.3.2 Secondary endpoint analyses

Key Secondary Endpoint

Objective response rate (ORR) defined as the proportion of patients with confirmed complete response (CR) or confirmed partial response (PR) is the key-secondary endpoint.

At the end of the second stage, the significance level for testing the null hypothesis $H_0: ORR \leq 5\%$ will be calculated as the exact binomial probability i.e. $\text{Prob}(X \geq s | n, p=0.05)$, where 's' is the observed number of patients achieving a confirmed objective response and 'n' is the total number of patients. A Wilson 90% confidence interval will be provided also.

Other Secondary Endpoints

Progression-free survival will be analysed by Kaplan-Meier method. Clinical deterioration without image-based progression will not be counted towards progression. Detailed censoring rule for PFS and sensitivity analysis will be specified in the Trial Statistical Analysis Plan (TSAP).

Disease control rate (DCR) defined as the proportion of patients with confirmed CR, PR or stable disease (SD) will be analysed similarly to ORR.

Duration of objective response is defined as the time from first documented CR or PR to the time of progression or death. Duration of objective response will be summarized descriptively.

Kaplan-Meier estimates of overall survival will be provided.

Tumor shrinkage from baseline will be summarized descriptively and by waterfall plot of the maximum percentage decrease from baseline of the sum of the longest diameters of target lesions will be presented.

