8.6 TRIAL MILESTONES

The **start of the trial** is defined as the date of the enrolment of the first patient in the whole trial.

The **end of the trial** is defined as the date of the last visit of the last patient in the whole trial ("Last Patient Out", LPO). And LPO is when the last patient has 24 months FU or evaluable for PFS6.

The **"Last Patient Drug Discontinuation"** (LPDD) date is defined as the date on which the last patient at an individual trial site ends trial medication (as scheduled per protocol or prematurely). Individual Investigators will be notified of SUSARs occurring with the trial medication until 30 days after LPDD at their site.

Early termination of the trial is defined as the premature termination of the trial due to any reason before the end of the trial as specified in this protocol.

Temporary halt of the trial is defined as any unplanned interruption of the trial by the sponsor with the intention to resume it.

Suspension of the trial is defined as an interruption of the trial based on a Health Authority request.

The IEC / competent authority in each participating EU member state will be notified about the trial milestones according to the respective laws.

A final report of the clinical trial data will be written only after all patients have completed the trial in all countries (EU or non-EU) to incorporate and consider all data in the report. The sponsor will submit to the EU database a summary of the final trial results within one year from the end of a clinical trial as a whole, regardless of the country of the last patient (EU or non-EU).

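### Sponsor removal after the primary analysis ends survival follow-up for patients still on afatinib; this contradicts the OS follow-up rule and, if used while others are still followed, pulls the late OS curve down

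*Protocol*

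**What the plan says.** **Removal.** Protocol 3.3.4.1 states: "The sponsor may remove patients from the study after completion of the primary efficacy analysis if the patient has access to afatinib study treatment" by another route. An end-of-treatment visit and a 30-day visit follow, "and then the patient will be considered to have completed the trial". The same section keeps vital-status collection for patients withdrawn for other reasons, if they agree.

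**Survival follow-up.** Protocol 6.2.3.3.2 states: "All patients will be followed-up for overall survival at 90 days intervals after the EoR visit or last follow-up for progression visit", until death, loss to follow-up or completion of the whole trial. Flow chart footnote 21 agrees. It adds: "For patients who progressed on treatment, the observation period for overall survival starts after the EoR visit".

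**Completion.** Protocol 6.2.3.4 lists four ways in which a patient completes the trial: planned follow-up finished, lost to follow-up, refusal, death. Sponsor removal is not among them.

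**End of trial.** Protocol 8.6 states: "LPO is when the last patient has 24 months FU or evaluable for PFS6". These are two different dates. Under the fourth reason in 3.3.4.2, the sponsor may also close the whole trial once the primary analysis is done and every patient has stopped treatment or can get afatinib elsewhere.

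**Analysis.** Protocol 7.3.2 says "Kaplan-Meier estimates of overall survival will be provided", and SAP 7.5.2 plans the same. SAP 6.6 censors patients of unknown vital status. The censoring table in SAP 7.5.2 covers PFS only; OS has no censoring rule, common cut-off or sensitivity analysis.

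**The concern.** A site cannot apply 3.3.4.1 and 6.2.3.3.2 to the same patient: one ends survival contact, the other requires it.

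The removal rule also selects on prognosis. Only a patient still taking afatinib can be moved to another supply, and such patients are mostly progression-free. Patients who have progressed stay in 90-day contact. Kaplan-Meier assumes that those censored at a given time have the same future risk as those who remain. Here the later risk sets would lose the patients doing best and keep those already progressed, so the late curve would be too low, and more so the better the drug works. OS is a named objective of an uncontrolled trial, so its late values will be read against outside data.

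**Working it through.** **1. The plan's own figures.** The documents give no OS figure to reproduce. The design figures do reproduce: with 70 patients and 60% against 40%, rejecting at 37 or more successes (one-sided 0.025) gives power 90.9%, and at 36 or more (0.05) gives 94.3%, as in protocol Table 7.7:1. Removal comes after the primary analysis, so it does not touch them.

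**2. Inputs for OS.**
- From the protocol: accrual 21 months (3.1.1); primary analysis when 70 Cohort A patients complete week 24 (7.4), so no earlier than 21 + 5.5 = month 26.5; 24-month reading of LPO (8.6), so month 21 + 24 = 45; PFS6 of 60% (7.7); published median PFS 2.9-4.0 months (1.1).
- Assumed: uniform entry; exponential PFS; exponential post-progression survival with median 5 or 8 months; on drug means not progressed; every on-drug patient removed and censored one month after the primary analysis.

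**3. Patients who could be removed.** A PFS6 of 60% corresponds to a median PFS of about 7.5 months, so λ = ln 2 / 7.5 = 0.0924 per month. The fraction on drug at month 26.5 is

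(e^(−5.5λ) − e^(−26.5λ)) / (21λ) = (0.6015 − 0.0864) / 1.941 = 0.265,

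or 18-19 of 70. At a median PFS of 4 months (λ = 0.1733) it is (0.3855 − 0.0101) / 3.639 = 0.103, about 7 of 70.

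**4. True OS in the model.** With post-progression median 5 months (rate 0.1386, 1.5 times λ), S(t) = 3e^(−0.0924t) − 2e^(−0.1386t). At 24 months this is 3 × 0.1088 − 2 × 0.0359 = 25.5%; the simulation with full follow-up gave 25.4%.

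**5. Kaplan-Meier OS with removal** (400,000 simulated patients per scenario, others followed to month 45):

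| Median PFS / post-progression (months) | 24-month OS, all followed | With removal | Median OS (months) |
|---|---|---|---|
| 7.5 / 5 | 25.4% | 20.2% | 15.0 to 14.4 |
| 7.5 / 8 | 36.7% | 32.0% | 18.7 to 17.8 |
| 4 / 5 | 11.8% | 10.2% | about 0.1 lower |

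In the first row, 18-month OS goes from 40.4% to 37.0%. If the primary analysis is completed two months after the last 24-week scan, the 24-month gap falls from 5.2 to 4.2 points in the first row and from 1.6 to 1.2 in the third.

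**6. Other assumptions.** A separate run used a two-month lag, Weibull PFS and post-progression medians of 3 and 6 months, with all on-drug patients removed. Points by which 24-month OS is too low:

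| PFS6 | Shape 1.0 | Shape 0.7 (heavier tail) |
|---|---|---|
| 40% | 1.4-1.5 | 3.3-3.5 |
| 60% | 4.3-4.7 | 5.9-6.9 |

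In the heavy-tailed 60% case the median falls by 0.4-1.2 months. Removing half of the on-drug patients gives roughly 35-50% of these gaps. The error was never upward; it was nil at 6 and 9 months and at most 0.6 point at 12 months.

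**7. PFS.** In the exponential model with median 7.5 months, Kaplan-Meier PFS at 12, 18 and 24 months was 33.0%, 18.9% and 10.8% without removal, and 33.0%, 18.8% and 10.7% with it. The difference is simulation noise.

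**The case against.** Much of the case against a stronger claim stands.

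- *A reader might infer that OS in this trial will be biased.* The documents do not support that. Removal is optional, needs another source of afatinib and comes only after the primary analysis. If the sponsor closes the whole trial at that point under 3.3.4.2, or if the PFS6 reading of LPO in 8.6 applies, everyone is censored at the same date and no bias arises. SAP section 7 triggers the final report when all patients are off afatinib and no 24-week assessments remain, and allows it to be merged with the primary report; removing the last on-drug patients could itself meet that trigger. With data cut three months after removal, the 24-month gap was 2.9 points, not 5.2. Against this, 8.6 ties the final report to all patients completing the trial, so the timing is unresolved, and the harmful sequence is permitted.
- *A reader might infer that PFS and DOR are biased in the same way.* They are not shown to be. For PFS, those censored are essentially the whole remaining risk set at one calendar date, which is ordinary administrative censoring. Adding an assumed 2% per month stopping drug independently of progression left PFS unchanged. Bias would require stopping drug to be prognostic, which was not examined. The longest responses do lose follow-up, but any data cut-off does that, and DOR is only summarised descriptively.
- *The effect is modest against sampling error.* With 70 fully followed patients the standard error of 24-month OS is about √(0.254 × 0.746 / 70) = 5.2 points, the size of the gap in the first scenario. That limits the consequence. It does not excuse a known one-directional error that is cheap to avoid.

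**Conclusion.** The contradiction between 3.3.4.1 and 6.2.3.3.2, footnote 21 and 6.2.3.4 is in the text and needs no assumption. The OS bias is conditional: it requires the removal right to be used while other patients stay in survival follow-up, as under the 24-month reading of LPO, and OS to be reported from those later data.

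Under those conditions, with exponential PFS and all on-drug patients removed, the 24-month estimate is too low by about 4-5 points if PFS6 is near 60%, and by about 1-2 points at a median PFS of 4 months. The median shifts by about 1 month at most. A heavier PFS tail makes the gaps larger; partial removal or an earlier data cut makes them smaller. Post-progression survival, the tail shape and the share removed are assumptions, not figures from the documents.

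PFS6, ORR, alpha, power and OS in the primary report are unaffected. OS is a descriptive secondary endpoint. This should be corrected before any removal takes place, but it does not threaten the trial's main result.

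**What to change.** 1. In protocol 3.3.4.1, state that removed patients leave protocol treatment visits but stay, with their consent, in the 90-day survival contact of 6.2.3.3.2 until LPO. Where that contact is kept, the OS bias disappears by construction. The cost is a telephone or written contact, already provided for, in roughly 7 to 18 patients under the exponential scenarios.
2. Align 6.2.3.4 with this, so that sponsor removal from treatment does not count as completing the trial.
3. Choose one LPO definition in 8.6, so that survival follow-up has the same planned end for everyone.
4. If the contact cannot be kept, add to SAP 7.5.2 an OS sensitivity analysis with one data cut-off for all patients, no later than the first removal. In the large simulation this restored 24-month OS to within 0.1 point. It is not free. In the first scenario with 70 patients it leaves about 2 at risk at 24 months (none in about 11% of runs) and raises the standard error to about 9.4 points. Its total error (root mean square) is then also about 9.4, against about 8.1 with removal and no common cut-off. It therefore belongs beside the main OS curve, with numbers at risk shown, and is second best to keeping the contact.

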3.3.4.2 Discontinuation of the trial by the sponsor

The sponsor may suspend recruitment after completing enrolment of the predefined 25 patients into stage 1 in the event of low likelihood to meet the criteria to move from Stage 1 to Stage 2.

Further to this, BI reserves the right to discontinue the trial overall or at a particular trial site at any time for the following reasons:

- Failure to meet expected enrolment goals overall or at a particular trial site
- Emergence of any efficacy/safety information invalidating the earlier positive benefit-risk-assessment that could significantly affect the continuation of the trial
- Violation of GCP, the CTP, or the contract disturbing the appropriate conduct of the trial
- The primary analysis has been completed and all patients have either ended study treatment or are eligible to receive afatinib under the conditions indicated in [section 3.3.4.1](#).

The Investigator/the trial site will be reimbursed for reasonable expenses incurred in case of trial termination (except in case of the third reason).

4. TREATMENTS

4.1 TREATMENTS TO BE ADMINISTERED

Patients will be treated with once daily oral dosing of afatinib. Patients will initially receive 40 mg tablets q.d.

4.1.1 Identity of BI investigational product(s) and comparator product(s)

Table 4.1.1: 1 Test product: afatinib

Substance (Brand Name):	Afatinib (Giotrif [®] / Gilotrif [®])
Pharmaceutical formulation:	Film-coated tablet
Source:	Boehringer-Ingelheim Pharma GmbH & Co. KG
Unit strength:	20 mg, 30 mg, 40 mg film-coated tablets (the dose of afatinib in the film-coated tablets is related to the free base equivalent to afatinib)
Posology	Once daily
Route of administration:	Oral

4.1.2 Method of assigning patients to treatment groups

After assessment of all in- and exclusion criteria, the medication number for each eligible patient will be assigned via Interactive Response Technology (IRT). Note that the medication number is different from the patient number (the latter is assigned at trial entry). To facilitate the use of the IRT, the investigator will receive all necessary instructions.

4.1.3 Selection of doses in the trial

Based on early phase clinical trials, a daily dose of 50mg in the monotherapy setting was identified as the dose for further development. This was used initially in EGFR TKI refractory population and several other phase II/III and proof of concept trials. Given a higher propensity of grade 3/4 AEs (especially diarrhoea), and no loss of efficacy especially in the EGFR mutation positive population dose was reduced to 40 mg in the pivotal phase III trials in EGFR mutated population ([P10-12524](#), [P10-12525](#), [P10-12529](#)). The 1200.22 (LUX- Lung 2) study enrolled 99 patients who started afatinib at 50 mg, and 30 patients starting at 40mg. While there was no substantial change in the occurrence of all AE grades for the two most frequent AEs, diarrhoea (96.7% in the 40 mg group compared to 93.9% in the 50 mg group) and rash/acne (90.0% in the 40 mg group compared to 94.9% in the 50mg group); there was a substantial difference in the occurrence of grade 3 AEs for diarrhoea (6.7% in the 40 mg group vs. 24.2% in the 50mg group) and rash/acne (6.7% in the 40 mg group and 28.3% in the 50 mg group). Neither group had grade 4 or 5 AEs reported for these terms ([P10-12524](#)).

In NSCLC and other indications, durable responses (>20 months) have been observed with daily dosing of afatinib of 40 mg and less ([P10-09678](#)) in a sensitive biomarker-positive population. The compound demonstrates efficacy at 4-12 nM in ERBB2AMP driven cell lines ([c01617169-04](#)), an EC50 between 10-20 nM in the ERBB2 mutated lung cancer cell line H1787, ([P09-00886](#)) irreversibly and covalently binds to its targets ([P12-09544](#)). Plasma levels reached in patients treated with 40 mg afatinib daily should be sufficient to treat ERBB2 driven tumours. The population in the trial will be naive to EGFR, ERBB2, ERBB3 targeted treatment. Patients with urothelial cancer will suffer from disease-associated comorbidities such as proteinuria, renal insufficiency, and side effects from previous anti-cancer treatment such as polyneuropathy or long-term effects from prior abdominal irradiations. Therefore afatinib will be used at a dose of 40 mg to optimize the tolerability and efficacy balance. The daily dose will be modified following careful monitoring of patient's drug-related adverse events and medication compliance.

4.1.4 Drug assignment and administration of doses for each patient

4.1.4.1 Administration of afatinib

Patients will take a single oral dose of afatinib each day starting at a dose of 40 mg, continuously, until progression of disease as confirmed by imaging according to RECIST 1.1 or patient's withdrawal of consent for continuation of treatment or other reasons requiring treatment discontinuation (see [section 3.3.4.1](#)). Dose reductions of afatinib can occur. See [Section 4.1.4.1.1](#).

The medication should be taken at approximately the same time each day without food (at least one hour before or at least three hours after a meal).

Missed doses of afatinib can be made up during the same day as soon as the patient remembers. However, if the next schedule dose is due within eight hours then the missed dose must be skipped. Patients with emesis must not take a replacement dose.

Medication will be dispensed in bottles containing 30 tablets at the beginning of each treatment course. For administrative purposes, a treatment course is defined as 28 days. Treatment will start when the patient is taking the first dose of medication and stop when the patient is diagnosed with disease progression or for any reason detailed in [Section 3.3.4](#), unless clinical benefit is obtained beyond PD (see [Section 3.2](#)). Study drug will be prescribed by the investigator through IRT system, and may be dispensed either by the investigator, site staff or affiliated pharmacy.

If dosing of whole tablets is not possible, afatinib tablets can also be dispersed in approximately 100 ml of non-carbonated drinking water. No other liquids should be used. The tablet should be dropped in the water, without crushing it, and occasionally stirred for up to 15 min until the tablet is broken up into very small particles. The dispersion should be drunk immediately. The glass should be rinsed with approximately 100 ml of water which should also be drunk. The dispersion can also be administered through a naso-gastric tube.

4.1.4.1.1 Dose reduction for afatinib

Treatment related AEs will be managed by treatment interruptions and subsequent dose reductions of afatinib according to the schedule described in [Table 4.1.4.1.1: 1](#). Dose reductions will apply to individual patients only. Once the dose has been reduced, it cannot be increased later.

To prevent the development of more severe adverse events, treatment related diarrhoea, nausea and vomiting or rash should be managed early and proactive as described in [Section 4.2](#).

Table 4.1.4.1.1: 1 Dose reduction scheme for afatinib

AE Type and CTCAE Grade	Action	Dose reduction scheme
Events related to study drug: 
 • Diarrhoea Grade 2 persisting for 2 or more consecutive days (48 hours) despite adequate anti-diarrhoeal medication/hydration • Reduced renal function caused by dehydration secondary to diarrhea to Grade 2 as measured by serum creatinine, proteinuria or decrease in glomerular filtration rate of more than 50% from baseline • Any drug related AE Grade ≥ 3 	Pause treatment until patient has recovered to Grade ≤ 1 or baseline ¹ . Resume treatment at reduced dose according to schedule opposite. If patient has not recovered to Grade ≤ 1 or baseline ¹ within 14 days study treatment must be permanently discontinued ² .	If patient was receiving 40 mg, resume treatment at a dose of 30 mg. If patient was receiving 30 mg, resume treatment at a dose of 20 mg. If patient was receiving 20 mg, discontinue afatinib.
Acute onset and/or unexplained worsening of pulmonary systems (dyspnoea, cough, fever)	Pause afatinib while clinical assessment to exclude ILD is completed.	If ILD is ruled out as a cause of symptoms, grade symptoms and relatedness and report as AEs. If AEs are not related, resume afatinib at current dose. If AEs are drug related, follow directions in row above. If ILD is confirmed, discontinue afatinib

¹ Baseline is defined as the CTCAE Grade at the start of treatment

² In the event that the patient is deriving obvious clinical benefit according to the investigator's judgement, further treatment with afatinib will be decided in agreement between BI Clinical Monitor and the investigator.

In the event of any unrelated adverse events, the investigator may choose to interrupt the medication for up to 14 days, but no dose reduction should occur. If the medication is interrupted for more than 14 days, the decision to continue with afatinib will be made by the BI clinical monitor in agreement with the investigator.

